4.4 Safety Objectives

The study aims to validate the overall implementation of the new chip with the ITE hardware. The study will test for unexpected behavior from the IMD and new risk factors to ensure safety of the devices before they are released to the market. A product questionnaire will be used to evaluate safety factors.

5. STUDY OUTCOMES

5.1 Primary Outcome

The primary outcome variable will be the speech scores measured with two speech tests and in three conditions: unaided, with the control (RMD), and with the new device (IMD). Speech scores should be equal to or better than those achieved with the RMD. A non-inferiority test will measure whether the location of the IMD microphones provide as good as or better speech scores than the location of the RMD microphones with a reference speech test. The second test uses different speech material to measure the microphone location effect and should generalize the results to wider listening conditions. The unaided condition will be used as a control of the IMD benefit if superiority cannot be shown.

5.2 Secondary Outcomes

The secondary outcome will be measured with questionnaires. A standardized questionnaire and two in-house questionnaires that ask questions specific to the study objectives will be completed by the test subjects. The standardized questionnaire provides a standard scoring method for comparing the overall performance of the two devices, and the in-house questionnaires will specifically address localization, comfort, and occlusion factors between the devices, as well as preference for the two styles.

5.3 Safety Outcomes

The in-house questionnaire will also ask questions regarding the safety of the devices to address the occurrence of unexpected noise or behavior from the devices. Unexpected behavior includes unprovoked feedback or whistling, distorted sounds or artefacts, discomfort, spontaneous muting or shutting off, unexplained warning signals or beeps, and louds sounds. The information provided from the field trial will alert the Sponsor to potential safety risks that should be addressed before releasing the device to the market.

6. STUDY DESIGN

6.1 General study design and justification of design

This is a controlled, randomized, open label, comparative clinical investigation conducted monocentric at the premises of Bernafon in Bern, Switzerland.

The exploratory study is based on a population of approximately 20 hearing impaired people that have a hearing loss appropriate for the IMD.

As an RMD, the subjects will be fit with Mermaid 9 BTEs during the trial. Additionally, a control situation will be the unaided test condition for speech testing.

There is no placebo or device that does not provide amplification. A single group assignment design is used with test subjects that have worn BTEs for approximately 6 months and will be fit with the RMD and IMD during the trial. The testing is unblinded as the main difference between the IMD and the RMD is hardware and therefore obvious to the end user that it's different.

A randomized test order will be used to test in a simulated environment. The test subjects will be tested using unaided and two aided conditions in a randomized manner for speech testing.

The participants are expected to participate for approximately 2-3 weeks for a combination of field and lab tests. There are two lab tests planned during which the participants will not spend more than 2 hours in the clinic (including breaks). The field test periods will not last more than 10 +/- 7 days.

The sequence will begin with the screening appointment in which participants are invited to the clinic for testing to determine if they are candidates for the trial. The entire test procedure will be explained, and they will be given a Patient Information and Informed Consent which will need to be signed, dated, and returned before any testing begins. If they choose to participate, a hearing test will be made to determine if they have an appropriate hearing loss, ear impressions will be made to make the custom fitting IMD, and the RMD will be fitted.

The following appointments will include fitting of the IMD, field tests during which they will wear the RMD and IMD, and lab tests in the clinic. There will be a total of 3 appointments, and each appointment will not exceed 2 hours. During the lab tests in the clinic they will participate in speech testing. Test subjects will be given questionnaires to complete at home and in the clinic.

After they have completed all appointments, the subjects will receive instructions about the continued use of their own hearing aids, and the reminder that they are welcome to come to the clinic for any maintenance or other follow-up of the hearing aids.

6.2 Methods of minimising bias

6.2.1 Randomisation

A single group assignment to the IMD will be used. The test order will be randomized based on list created by the statistician. This means that for the speech tests the subjects will be randomized by the condition. This reduces bias by using a different starting and ending condition as the last condition has a higher chance of scoring higher due to a learning effect from the speech test. The list will not be concealed, but should be in the ISF so that the PI knows in which condition order to test each subject.

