3.8 Justification of choice of study population

The choice of study population was determined by the goal of the study. The intended purpose of the study is to compare current Bernafon device performance against the new device and not the overall effect of amplification. Therefore, only participants that are hearing impaired and experienced hearing aid users will be included. Bernafon has its own database of test subjects that are used for clinical trials. They are current hearing aid users that use the Bernafon clinic for adjustments to fittings and general maintenance of their hearing aids performed by the audiologists working at Bernafon. These test subjects do not consist of employees of Bernafon or family members of employees. The test subjects for the current study will be chosen from this internal subject database.

The comparison between devices shall be made with experienced hearing aid users. It is important to compare the performance of the devices and the subjective opinions of the intended users. Testing normal hearing participants would not contribute information to this study. Test participants must be able to sign and understand the consent form to be included in the study. For emergency situations, the following applies:

-The standard procedure is to recommend that a subject see the ENT with whom they have an established relationship. If a subject does not have an ENT then it is agreed with [name] (Inselspital, Bern) that, if necessary, subjects from the trial could be referred to him.

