7.3 Assignment to study groups

For the field tests the allocation is single group; therefore, all the test subjects will be assigned to the same group. The initial field test will be with the RMD and the second with the IMD, as it will take time

to have the IMD made by the lab.

For the lab tests the assignment to the test condition order will be randomized by the statistician. The test condition order will be randomized using a latin square design. This will minimize bias created when one test condition is tested in the final or last position all the time.

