9.3.2 Fitting/Second Visit

Fitting Visit, Day 10 +/-7: Otoscopy is performed, and the subjects are fitted with the IMD. Output of the IMD is measured, and the fitting adjusted, if necessary, to better match the electroacoustic output of the previously worn, RMD. They are randomized for the speech testing. Speech tests are made with the OLSA in three conditions: unaided, aided with RMD, and aided with IMD. The subjects return the RMD and held until the third appointment for further speech testing. The subjects return the completed questionnaires from the first visit and are given two more questionnaires (APHAB and product) to complete at home. They are given instructions about the IMD and an IFU with information about the IMD. They are scheduled for the third visit. Any AEs are reported in the CRFs.

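### The condition-order list is left open in the investigator site file although the tester needs only one subject's order at the session: a minor weakness that is cheap to close

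*Protocol*

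**What the plan says.** Section 6.2.1 gives the source of the order: "The test order will be randomized based on list created by the statistician". It gives the reason for randomising: "the last condition has a higher chance of scoring higher due to a learning effect from the speech test". It then says: "The list will not be concealed, but should be in the ISF so that the PI knows in which condition order" to test each subject.

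Section 7.3 repeats that the statistician assigns the order and adds the method: "The test condition order will be randomized using a latin square design". Field use is not randomised. There is one group, and the RMD is always worn first.

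Section 9.3.2 describes visit 2. After the IMD has been fitted and its output matched to the RMD, it says of the subjects: "They are randomized for the speech testing". The OLSA follows in all three conditions. Section 9.3.3 does the same for the GÖSA at visit 3. Section 6.2.2 says that testing is unblinded.

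On recruitment, section 3.8 says: "The test subjects for the current study will be chosen from this internal subject database". It does not name the role that chooses. Section 2.8 says that subject numbers are given when people join the pool, which is before this trial.

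**The concern.** The order list is the protocol's stated protection of the primary OLSA comparison against learning, and the paragraph that introduces it also opens it. The reason given, that the PI must know the order, is met by knowing one subject's order when that subject is tested. It does not require sight of the orders still to come. The visit 2 description places randomisation after fitting and output matching, but an open list allows the order to be known before either step.

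A Latin square removes learning from the mean IMD-RMD difference if subjects fall into the orders independently of how much they learn. If those expected to learn more were placed where the IMD follows the RMD, part of the learning would remain in the difference that is compared with the 1 dB margin.

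**Working it through.** **The plan's own figure.** Section 11.2 uses n = (σ(z₁₋α + z₁₋β)/δ)² with σ = 1.6 dB, δ = 1 dB, α = 0.05 and power 0.80. This gives (1.6 × (1.645 + 0.842)/1)² = 15.83, rounded up to 16. The figure reproduces, and concealing the list does not change it.

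**How learning enters.** Let L be a subject's gain in dB per test position and d the position of the IMD minus the position of the RMD. Learning adds d × L to that subject's IMD-RMD difference in benefit. In one cyclic square (U = unaided, R = RMD, I = IMD) the orders are:

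| Order | d |
|---|---|
| U-R-I | +1 |
| R-I-U | +1 |
| I-U-R | -2 |

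**Common learning.** The d values sum to zero over a complete square. If every subject has the same L, the mean shift is zero whoever receives which order. Simulation at n = 15 and n = 18 gave 0.00 dB with and without matching. At n = 16 the last square is incomplete. With 11 subjects at +1 and 5 at -2, the shift is (11 - 10)/16 × 0.5 = 0.03 dB for L = 0.5 dB and 0.06 dB for L = 1.0 dB. This comes from the incomplete square, not from the open list.

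**Learning that differs between subjects.** The protocol gives no size for learning, so these inputs are assumptions: mean L of 0.5 dB per position, between-subject SD s of 0.3 to 0.5 dB, and a prediction of L with correlation r of 0.3 to 0.5. The predicted weakest third is placed in the IMD-first order. For a large sample the shift is 3 × φ(z₁/₃) × r × s = 3 × 0.3636 × r × s = 1.09 × r × s.

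| s (dB) | r | 1.09 × r × s (dB) | Simulated, n = 16 (dB) |
|---|---|---|---|
| 0.3 | 0.3 | 0.10 | 0.12 |
| 0.3 | 0.5 | 0.16 | 0.18 |
| 0.5 | 0.3 | 0.16 | 0.18 |
| 0.5 | 0.5 | 0.27 | 0.28 |

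The unmatched value at n = 16 is 0.03 dB.

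**Error at the margin.** With n = 16 and SD fixed at 1.6 dB, the noncentrality is shift × √16/1.6 = 2.5 × shift, on 15 degrees of freedom. Shifts of 0.10, 0.16 and 0.27 dB give noncentralities of 0.25, 0.40 and 0.675. The one-sided 5% error becomes 8.0%, 10.3% and 15.9%.

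These error rates leave out the extra spread that the order effects add to the differences. A simulation that includes it, with n = 15 or 18, s of 0.25 to 0.5 dB and mean L of 0.5 or 1.0 dB, gave about 3% to 9% at r = 0.3. Perfect prediction, which is not realistic, gave shifts of 0.26 to 0.52 dB and error of 7% to 34%.

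**The case against.** A reader might infer that one person picks, books and tests the subjects, sees every coming order and can steer who gets which. The protocol does not say so. Sections 3.8 and 7.2 have subjects chosen without naming the role, and no section says who books visits. The wording of 6.2.1 fits a list already tied to named subjects at least as well as a queue of open slots. Eligibility is settled at visit 1, and visit 2 follows 10 +/- 7 days later, so choosing whom to enrol does not by itself decide who meets which row.

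A reader might also infer the selection bias familiar from unconcealed parallel-group trials. It does not arise here, because every subject is tested with both devices at the same visit and nobody can be moved towards or away from a device. Nor is concealment the only protection. The Latin square, the paired comparison and the output matching all remain.

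These points stand, and they limit the size of the concern. They do not remove it. Section 12.1.1 lists the PI as author of the inclusion and exclusion entries and of the OLSA results. Section 7.4 lets the investigator withdraw subjects for unreliable responses. Subjects come from a database maintained through the sponsor's own clinic. Nothing ties list rows to subject numbers, and if rows did follow pool numbers, an open list would show each candidate's order before invitation. The protocol neither shows steering nor rules it out.

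**Conclusion.** The point holds as a minor one. Section 6.2.1 opens the only randomised element of an unblinded trial for a reason that does not require it.

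The likely effect on the primary result is a small part of the 1 dB margin. It is about zero without matching of subjects to orders, and about 0.1 to 0.3 dB with it. The larger figures need all of the following together: learning that differs between subjects, someone able to predict it, freedom to match subjects to orders, and consistent use of that freedom in favour of the IMD. The protocol documents none of these, and the learning values are assumptions. The 15.9% error is the extreme corner of the assumed range and should not be read as an estimate for this trial.

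The unblinded tester and subject are a separate concern that a concealed list would not cure.

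**What to change.** Replace the last sentence of 6.2.1 with wording to this effect:

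- The statistician holds the list and ties each row to an enrolled subject before that subject's visit 2 is scheduled.
- Each subject's order is disclosed, for example by a sealed numbered envelope, only at visit 2 after both devices are fitted and output-matched, and at visit 3 immediately before the GÖSA.
- The order actually used is logged at each visit.
- The full list is filed in the ISF after the last subject's last test.

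Rows should not be handed out in sequence of attendance from complete 3 × 3 squares, because a tester who has seen two orders of a square can deduce the third. Tying rows to subjects beforehand avoids this.

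The cost is one paragraph of protocol text, a set of envelopes (two per subject, so 2 × 20 = 40 for about 20 subjects) and one log entry per visit. The sample size stays at 16, and the tester still has the order when it is needed.

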6.2.2 Blinding procedures

The testing will be unblinded as the differences in the hardware of the device make it impossible to blind.

6.2.3 Other methods of minimising bias

A validated questionnaire to compare the overall performance between the IMD and RMD will be used to minimize bias. Additionally, the RMD will be programmed to a standard first fit setting that will be consistent with the electroacoustic fitting of the IMD. The RMD will be fit at the first appointment when the ear impressions are made for the IMD. They will wear the RMD for approximately 10 +/- 7 days with the standard fitting before returning to the clinic for the IMD fitting. The equivalent fitting will reduce bias that subjects may otherwise have toward their previous BTE fitting.

6.3 Unblinding Procedures (Code break)

N/A, the study is performed unblinded.

7. STUDY POPULATION

The study will take place in the clinic at Bernafon AG in Bern. No other sites will be used for the testing.

7.1 Eligibility criteria

Participants fulfilling all of the following inclusion criteria are eligible for the study:

- All classifications of hearing loss (sensorineural, conductive, mixed)
- If the hearing loss is conductive or mixed, it must be approved for amplification by a physician
- All shapes of hearing loss (flat, sloping, reverse slope, notch)
- Hearing loss severity ranging from mild to severe
- German speaking
- Both genders
- Ages 18 and older
- Ability and willingness to sign the consent form
- Current BTE hearing aid user

The presence of any one of the following exclusion criteria will lead to exclusion of the participant:

- Contraindications for amplification
- Active ear disease
- Inability to follow the procedures of the study due to language problems, psychological disorders, dementia, or other cognitive problems
- A reduced mobility making them unable to attend weekly study appointments
- A reduced ability to describe auditory impressions and the usage of the hearing aids
- Uncooperative so that it is not possible to record a valid pure tone audiogram
- A strongly reduced dexterity
- Central hearing disorders
- Bernafon employees
- Family members of Bernafon employees

7.2 Recruitment and screening

Bernafon has its own database of test subjects that use the Bernafon clinic for updated fittings and general maintenance of their hearing aids. These test subjects do not consist of employees of Bernafon or family members of employees. The test subjects for the current study will be chosen from the internal subject database. Bernafon does not advertise as a method of recruiting participants. Participants are collected and added to the database by word of mouth. If a current person from the database knows of another person with hearing loss they may give them the contact information of an audiologist within Bernafon. The person can then contact Bernafon if they wish to have a hearing test and determine if they're eligible to participate in a study. They are given a diagnostic audiological exam to determine if they have a hearing loss and the severity. If there are any medical indications it is recommended that they see a physician and then return if there are no contra-indications for hearing aids. During the hearing exam and medical history discussion it is determined whether the person is cognitively able to act on their own behalf. Additionally, if the person comes alone or if they are accompanied will help to determine their level of independence. If there is a study that is ready to take place then that will be explained at this time including an estimation of how much time/number of appointments would be required of them. If there is no immediate study planned, the normal study process will be explained to the subjects and they will be put on a waiting list. It is explained that the general compensation for their time is by means of a box of batteries and cleaning accessories.

7.3 Assignment to study groups

For the field tests the allocation is single group; therefore, all the test subjects will be assigned to the same group. The initial field test will be with the RMD and the second with the IMD, as it will take time

to have the IMD made by the lab.

For the lab tests the assignment to the test condition order will be randomized by the statistician. The test condition order will be randomized using a latin square design. This will minimize bias created when one test condition is tested in the final or last position all the time.

7.4 Criteria for withdrawal / discontinuation of participants

Participants are allowed to withdraw from the study at any time and for any reason. They do not have to share the reasons with the investigator. They will be asked to return the IMD. If the decision to withdraw is made by the investigator, the PI will inform the subject in person that they are no longer needed for the study. Reasons for withdrawing a participant from the study could be for non-compliance during testing, unreliable responses, medical reasons such as an ear infection, or the study may need to be stopped or postponed. Any data gathered from these subjects will be used for the current study. All data will remain encoded because results are only recorded using the identification code of the subject. There are normally at least five “back-up” test participants on the list to replace those that withdraw or are withdrawn. The “back-up” participants have already been screened and deemed to be appropriate for the study.

8. STUDY INTERVENTION

8.1 Identity of Investigational Products (medical device)

The treatment will be approximately 2 weeks of use with the IMD during which they will not use the RMD. During the study they will stop using the RMD and switch to the IMD for the assigned period.

There will be lab tests during which the participants will use the RMD and the IMD, for up to 2 hours at a time during testing in the clinic.

8.1.1 Experimental Intervention (medical device)

The investigation product (IMD) is a medical device. It is a new version of a Bernafon hearing device. The name is Mermaid 9 ITE. The Mermaid 9 BTE style was released to the market in early 2017. The Mermaid 9 ITE does not deviate from the current commercial product except for the hardware style. The ITE is fitted completely in the ear canal and concha of the ear while the BTE style fits with the body of the device over the ear, and a dome or earmold inside of the ear canal. Performance of the IMD is expected to be the same as the RMD. They are non-invasive devices. The hearing aid is worn inside the ear canal and is made from non-toxic plastic with an acrylic coating. A comparison of the hardware styles is shown in Figure 1.

Figure 1. Mermaid 9 ITEs (left) and Mermaid 9 BTEs (right).

8.1.2 Control Intervention (comparator medical device)

The Reference Medical Device (RMD) is the Mermaid 9 BTE as shown above in Figure 1. It is a CE marked hearing aid that was released to the market in 2017. The intended purpose of both devices is the same-to amplify sounds. The strength of the amplification is programmed according to the subject's individual hearing loss. There is no placebo treatment used as the study uses the accepted standard treatment for hearing loss as the control. The RMD and the IMD will be programmed based on each participant's hearing loss. The amplification will be set for both devices as determined using the REM data. The output amplification will be tested for both the RMD and the IMD to ensure that they are similar.

8.1.3 Packaging, Labelling and Supply (re-supply)

The IMD is labelled by printing the name of the device directly onto the device. There is an individual serial number that also printed on the device. The production batch can be tracked through this serial number. The hearing aids are shipped in a box with a label on the outside of the box that states the name of the product, the serial number, and a short description. Inside the box is a case that houses the hearing aids. The HCP removes the case from the box, and the case is generally given to the end user in which to place the hearing aids whenever they are not worn. The packaging and labelling are the same for the IMD and the RMD.

